### **5.3 Equitable participant selection**

**45 CFR 46.111 (a) 3 and 21 CFR 56.111 (a) 3: Subject selection is equitable**

This protocol has specific inclusion and exclusion criteria for investigators to follow in admitting participants into the protocol. Participants are selected because of these criteria and not because of positions of vulnerability or privilege. Investigators are required to maintain screening and enrollment logs to document participants who screened into and out of the protocol and for what reasons.

### **5.4 Appropriate informed consent**

**45 CFR 46.111 (a) 4 and 5 and 21 CFR 56.111 (a) 4 and 5: Informed consent is sought from each prospective subject or the subject's legally authorized representative as required by 45 CFR 46.116 and 21 CFR Part 50; informed consent is appropriately documented as required by 45 CFR 46.117 and 21 CFR 50.27**

The protocol specifies that informed consent must be obtained before any study procedures are initiated and assessed throughout the trial (see Section 9.1). Each site is provided training in informed consent by the CoVPN and is required to have a Standard Operating Procedure (SOP) on the informed consent process. The CoVPN requires a signed consent document for documentation, in addition to chart notes or a consent checklist.

### **5.5 Adequate safety monitoring**

**45 CFR 46.111 (a) 6 and 21 CFR 56.111 (a) 6: There is adequate provision for monitoring the data collected to ensure the safety of subjects.**

This protocol has extensive safety monitoring in place (see Section 11). Safety is monitored daily by CoVPN clinical staff and routinely by the CoVPN 3008

(Ubuntu) PSRT. In addition, an independent DSMB periodically reviews study data, including unblinded study data if/when needed.

## **5.6 Protect privacy/confidentiality**

**45 CFR 46.111 (a) 7 and 21 CFR 56.111 (a) 7: There are adequate provisions to protect the privacy of subjects and maintain the confidentiality of data.**

Privacy refers to an individual's right to be free from unauthorized or unreasonable intrusion into his/her private life and the right to control access to individually identifiable information about him/her. The term "privacy" concerns research participants or potential research participants as individuals whereas the term "confidentiality" is used to refer to the treatment of information about those individuals. This protocol respects the privacy of participants by informing them about who will have access to their personal information and study data (see [Appendix A](#)). The privacy of participants is protected by assigning unique identifiers in place of the participant's name on study data and specimens. In addition, each staff member at each study site in this protocol signs an Agreement on Confidentiality and Use of Data and Specimens with the CoVPN. In some cases, a comparable confidentiality agreement process may be acceptable. Each study site participating in the protocol is required to have a standard operating procedure on how the staff members will protect the confidentiality of study participants.

## **5.7 Pregnant participants**

45 CFR 46.203 and 45 CFR 46.204: There are adequate protections for pregnant women, human fetuses, and neonates involved in research.

The NIH is mandated by law to ensure that pregnant women and children be included in clinical research when appropriate. This study responds to that mandate and will provide valuable research data on the clinical and immunologic outcomes in pregnant women. Per the US Code of Federal Regulations (CFR), site IRBs/ECs must consider the potential risks and benefits to maternal and fetal participants as described in 45 CFR 46 Subpart B (for pregnant women, fetuses, and neonates). In addition to the US regulations cited above, sites not in the US must also comply with all applicable local and national guidelines and regulations.

## 6 Statistical considerations

### 6.1 Summary of statistical design

The statistical design primarily aims to evaluate 1) in the pre-Month 6 stage, the relative risk of COVID-19 and severe COVID-19 between the PLWH vaccine-only immunity group who are SARS-CoV-2 negative at enrollment, and assigned to receive 2 doses of pre-Month 6 vaccinations, and the PLWH hybrid immunity group who are SARS-CoV-2 positive at enrollment and assigned to receive 1 dose of pre-Month 6 vaccination (i.e., co-primary objectives 1 and 2) and; 2) in the post-Month 6 stage the relative risk of COVID-19 and severe COVID-19 between the mRNA-1273 and mRNA-1273.222 randomized arms (i.e., co-primary objectives 3 and 4). In the pre-Month 6 stage, the evaluation considers follow-up after enrollment until the Month 6 dose; in the post-Month 6 stage, the evaluation considers follow-up after the Month 6 dose until the end of study.

Severe COVID-19 is included as a coprimary endpoint, which recognizes the importance of evaluating severe COVID-19 in PLWH. Given uncertainty in the rate of severe COVID-19 at the time of the primary analysis, an adaptive decision based on the treatment-blinded number of severe COVID-19 endpoints is made of whether to retain severe COVID-19 as a primary endpoint or to change it to a secondary endpoint. In addition, as secondary objectives of this trial, the relative risk of COVID-19 and severe COVID-19 will be evaluated in Groups 1 and 3 combined vs. Groups 2 and 4 combined, accounting for baseline HIV-1 serostatus.

For the pre-Month 6 stage, given that the analysis groups defined by HIV and SARS-CoV-2 statuses, and the number of vaccinations received are not randomized, and the assignment of individuals to study groups is known to participants and study staff, the study objectives are assessed using methods that adjust for measured potential confounder variables (see Section 6.4.3). For the post-Month 6 stage, because participants were randomized at baseline to the assignment of the two different Month 6 vaccinations within each of Groups 1-4, adjustment for potential confounder variables is only considered for the assessment of secondary objectives, not the primary objectives.

### 6.2 Definitions of study cohorts for analysis

Throughout the protocol, unless otherwise noted, baseline SARS-CoV-2 negative indicates both (anti-Spike and anti-Nucleocapsid) seronegative and virus detection negative, and SARS-CoV-2 positive indicates either (anti-Spike or anti-Nucleocapsid) seropositive or virus detection positive of participants' samples collected prior to the first vaccination. Of note, baseline SARS-CoV-2 anti-Spike (anti-S) sero-status (which does not account for virus or anti-Nucleocapsid (anti-N) detection) is used to determine treatment group assignment, not analyses cohorts. The definitions of study cohorts that will be analyzed for addressing various study

objectives are provided in [Table 6-1](#) below. The Full Analysis Set (FAS) and the Safety Subset (SS) will be the cohorts for the primary safety analyses according to the treatment that participants actually received. The subgroups of FAS participants will be the cohort for the pre-Month 6 stage primary efficacy analyses. The subgroups of Per-Protocol (PP) participants will be the cohort for the post-Month 6 stage primary efficacy analyses. The subgroups of PP participants that are sampled for cellular and humoral immunogenicity and immune correlates analyses comprise the Immunogenicity Subset (IS). In addition to those measured at Month 7 (one month after the Month 6 dose) across all groups in the IS, immune responses at Month 1 (one month after dose 1) among baseline SARS-CoV-2 seropositive participants in Groups 2 and 4 and immune responses at Month 2 (one month after the second dose) among baseline SARS-CoV-2 seronegative participants in Groups 1 and 3 will be used to characterize vaccine-induced immunogenicity proximal to vaccination. Immunogenicity at baseline (Month 0) and at the Month 6 visit immediately prior to the Month 6 dose, and durability of immunogenicity at Months 12 and 18 will also be assessed across all groups in the IS.

**Table 6-1 Analysis Cohorts and Corresponding Primary, Secondary or Exploratory Objectives**

Cohort	Definition	Objectives
Full Analysis Set (FAS)	All randomized participants with $\geq 1$ administration of study product	Primary objective 5
• Subgroup FAS.Grp1	• PLWH who are SARS-CoV-2 negative  at baseline (Group 1) in the FAS	Primary objectives 1 & 2 Secondary objectives 1-2, 10 Exploratory objectives 1-5
• Subgroup FAS.Grp2	• PLWH who are SARS-CoV-2 positive  at baseline (Group 2) in the FAS, who received either 1 or 2 pre-Month 6 vaccination doses	Primary objectives 1 & 2 Secondary objectives 1-2, 10 Exploratory objectives 1-5
• Subgroup FAS.Grp3	• People who are HIV-1 seronegative and SARS-CoV-2 negative  at baseline (Group 3) in the FAS	Secondary objectives 2, 10 Exploratory objectives 1-5
• Subgroup FAS.Grp4	• People who are HIV-1 seronegative and SARS-CoV-2 positive  at baseline (Group 4) in the FAS, who received either 1 or 2 pre-Month 6 vaccination doses	Secondary objectives 2, 10 Exploratory objectives 1-5
Safety Subset (SS)	Participants in the FAS who are sampled for solicited and unsolicited AE assessment	Primary objective 5
• Subgroups SS.Grp1-4	• Groups 1-4 participants in the SS	Primary objective 5
Per-Protocol (PP)	Participants in the FAS who received all planned immunizations according to the current study schema and have no major protocol violations 	Primary objectives 3 & 4
• Subgroup PP.Grp1	• Group 1 PP participants who are SARS-CoV-2 negative  at baseline	Secondary objectives 3-8 Exploratory objectives 1-5
• Subgroup PP.Grp2	• Group 2 PP participants who are SARS-CoV-2 positive  at baseline, receiving 1 or 2 pre-Month 6 vaccination doses	Secondary objectives 3-5, 8 Exploratory objectives 1-5
• Subgroup PP.Grp3	• Group 3 PP participants who are SARS-CoV-2 negative  at baseline	Secondary objectives 4-8 Exploratory objectives 1-5
• Subgroup PP.Grp4	• Group 4 PP participants who are SARS-CoV-2 positive  at baseline, receiving 1 or 2 pre-Month 6 vaccination doses	Secondary objectives 4-5, 8 Exploratory objectives 1-5
Immunogenicity Subset (IS)	Participants who are sampled into the subset for measuring humoral immunologic markers  at Months 0, 1 (Groups 2 and 4 only), 2 (Groups 1 and 3 only), 6, 7 and 12.	Secondary objective 9 Exploratory objectives 4-5
• Subgroups IS.Grp1-4	• Groups 1-4 participants in the IS	
• Subgroup IS.PBMC.Imm.Grp1-4	• Groups 1-4 participants in the IS who are also sampled into the PBMC Immunogenicity subset for measuring cellular immunologic markers at Months 0, 1 (Groups 2 and 4 only), 2 (Groups 1 and 3 only), 6, 7 and 12.	
• Subgroup IS.PBMC.Cor.Grp1-2	• Groups 1 and 2 participants in the IS who are also sampled into the PBMC Immune Correlates subset for measuring cellular immunogenicity markers at Months 0, 1 (Group 2 only), 2 (Group 1 only), and 7.	

 SARS-CoV-2 negative is defined by both seronegative and virus detection negative or by seronegative alone if missing virus detection test results.

 SARS-CoV-2 positive is defined by seropositive and/or virus detection positive.

 Major protocol violations are protocol deviations that compromise study integrity; for example, protocol deviations related to collection or reporting of data necessary to interpret the primary efficacy endpoint.

 Immunologic markers measured will include binding antibody and neutralizing antibody markers.

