### 3 Objectives and endpoints

All symptomatic COVID-19 endpoints will be evaluated using two case definitions, one used in the COVE study (8, 12) and the other using a case definition based on criteria from the CDC (144, 145). The first two primary objectives count COVID-19 and severe COVID-19 endpoints starting 14 days after the last pre-Month 6 dose until the Month 6 dose in the pre-Month 6 stage, and compare the rate of these endpoints between adult PLWH with vaccine-only immunity vs. adult PLWH with hybrid immunity. The third and fourth primary objectives count COVID-19 and severe COVID-19 endpoints starting 14 days after dose 3 until the end of follow-up in the post-Month 6 stage, and compare the rate of these endpoints in adult PLWH who were randomized and received mRNA-1273 vs. mRNA-1273.222 vaccine. Secondary objective 1 compares rates of COVID-19 and severe COVID-19 in the pre-Month 6 stage during a different period of follow-up: starting 14 days after dose 2 for participants who are SARS-CoV-2 negative at baseline and starting 14 days after dose 1 for participants who are SARS-CoV-2 positive at baseline. Answers to primary objectives 1 and 2 will be available earlier than answers to primary objectives 3 and 4, such that essentially, the trial has two stages answering study questions comparing hybrid vs. vaccine-only immunity, and comparing two different month 6 vaccinations.

Primary Objectives	Primary Endpoints
1. PRE-MONTH 6 STAGE : to assess the relative risk of symptomatic COVID-19 in Group 1 (PLWH who are SARS-CoV-2 negative at baseline) who receive a 2-dose mRNA-1273 vaccine regimen vs. in Group 2 (PLWH who are SARS-CoV-2 positive at baseline) who receive a 1-dose mRNA-1273 regimen, counting endpoints starting 1 day after Month 0 dose until Month 6 dose.	1. COVID-19: Positive result of acute SARS-CoV-2 infection as assessed by nucleic acid amplification testing (NAAT) of a nasal swab and the presence of a prespecified symptom or symptoms (see footnotes 2 and 3)
2. PRE-MONTH 6 STAGE : to assess the relative risk of severe COVID-19 in Group 1 (PLWH who are SARS-CoV-2 negative at baseline) who receive a 2-dose mRNA-1273 vaccine regimen vs. in Group 2 (PLWH who are SARS-CoV-2 positive at baseline) who receive a 1-dose mRNA-1273 regimen, counting endpoints starting 1 day after Month 0 dose until Month 6 dose.	2. Severe COVID-19: COVID-19 that meets the criteria listed in footnote 4

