3. POST-MONTH 6 STAGE : to assess the relative risk of symptomatic COVID-19 after the Month 6 dose among those who received mRNA-1273 at Month 6 vs. those who received mRNA-1273.222 at Month 6, counting endpoints at least 14 days after the Month 6 dose until end of follow up.	3. COVID-19: same as above
4. POST-MONTH 6 STAGE : to assess the relative risk of severe COVID-19 after the Month 6 dose among those who received mRNA-1273 at Month 6 vs. those who received mRNA-1273.222 at Month 6, counting endpoints at least 14 days after the Month 6 dose until end of follow up.	4. Severe COVID-19: same as above

Primary Objectives	Primary Endpoints
5. To assess the safety and tolerability of mRNA-1273 and mRNA-1273.222 in adults who are at risk of severe COVID-19 in both the pre-Month 6 and post-Month 6 stages.	5. Adverse events: Solicited and unsolicited AEs collected for a subset of study participants. Serious adverse events (SAEs), adverse events of special interest (AESIs), collected for all participants throughout the study

 HIV-infection status and SARS-CoV-2 status are confirmed for each participant based on testing of samples collected during screening (serology) and at enrollment (NAAT). SARS-CoV-2 negative indicates both NAAT negative and serology negative.

 To be considered as a case of COVID-19 using the COVE case definition for the evaluation of the Primary Efficacy Endpoint, the following criteria must be met:

1. The participant must have experienced at least TWO of the following systemic symptoms: Fever ( $\geq 38^{\circ}\text{C}$ ), chills, myalgia, headache, sore throat, new loss of taste or smell, OR
2. The participant must have experienced at least ONE of the following respiratory signs/symptoms: cough, shortness of breath or difficulty breathing, OR clinical or radiographical evidence of pneumonia; AND
3. The participant must have at least 1 nasal swab (or respiratory sample, if hospitalized) positive for SARS-CoV-2 by NAAT within 14 days following the above systemic or respiratory symptoms.

 To be considered as a case of COVID-19 using the CDC-derived case definition for the evaluation of the Primary Efficacy Endpoint, the following criteria must be met:

1. The participant must have experienced at least ONE of the following systemic symptoms: Fever ( $\geq 38^{\circ}\text{C}$ ), chills, myalgia, headache, sore throat, new loss of taste or smell, OR

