## 9.6 COVID-19 Symptom Visits and COVID-19 Post-diagnosis Schedule

The following procedures will be performed at the COVID-19 Symptom Visits for participants meeting the criteria for COVID-19 Symptom Visits outlined in Section 9.5. Participants with COVID-19 confirmed by SARS-CoV-2 NAAT test, regardless of symptoms, enter a postdiagnosis schedule (see [Appendix J](#)) to assess the presence, types, severity, and duration of potential COVID-related symptoms as well as duration of viral shedding. Participants found to have a positive SARS-CoV-2 NAAT test as part of a regularly scheduled visit outlined in Section 9.3 will also enter the postdiagnosis schedule (see [Appendix J](#)).

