Month 6 SARS-CoV-2 status, a new variable for Part B analyses, is defined as hybrid immunity or vaccine immunity. Specifically, a participant is said to have Month 6 hybrid immunity if they have any evidence of prior SARS-CoV-2 infection up to the Month 6 visit as defined by meeting any of the following criteria: 1) baseline overall SARS-CoV-2 status is positive as defined above, 2) at least one NAAT result at or prior to Month 6 is positive, or 3) at least one CLS at or prior to Month 6 is positive. Otherwise, a participant is said to have Month 6 vaccine immunity. In another word, a participant is considered having only vaccine immunity at Month 6 if absent of any evidence of SARS-CoV-2 infection from enrollment up to Month 6. Of note, POCS results are expected to be available from all participants only for their M0 samples; CLS results are expected to be available from all participants for both their M0 and M6 samples.

Lastly, recent SARS-CoV-2 infection status at Month 6, another new variable for Part B analyses,

Table 1: **Panel A:** Empirical probability that CLS or NAAT test result was positive conditional on different configurations of the other two test results among 13,857/14,040 participants with all three test results measured at baseline. **Panel B:** Empirical probability that CLS or NAAT was positive conditional on POCS test result among 13,929/14,040 participants with both CLS and POCS test results and among 13,915/14,040 participants with both NAAT and POCS test results, respectively.

	Value
Panel A	
$P(\text{CLS} = 1 \text{POCS} = 0 \ \& \ \text{NAAT} = 0)$	0.29
$P(\text{CLS} = 1 \text{POCS} = 1 \ \& \ \text{NAAT} = 0)$	0.58
$P(\text{CLS} = 1 \text{POCS} = 1 \ \& \ \text{NAAT} = 1)$	0.80
$P(\text{CLS} = 1 \text{POCS} = 0 \ \& \ \text{NAAT} = 1)$	0.59
$P(\text{NAAT} = 1 \text{POCS} = 0 \ \& \ \text{CLS} = 0)$	0
$P(\text{NAAT} = 1 \text{POCS} = 1 \ \& \ \text{CLS} = 1)$	0.07
$P(\text{NAAT} = 1 \text{POCS} = 1 \ \& \ \text{CLS} = 0)$	0
$P(\text{NAAT} = 1 \text{POCS} = 0 \ \& \ \text{CLS} = 1)$	0.23
Panel B	
$P(\text{CLS} = 1 \text{POCS} = 0)$	0.32
$P(\text{CLS} = 1 \text{POCS} = 1)$	0.59
$P(\text{NAAT} = 1 \text{POCS} = 0)$	0.07
$P(\text{NAAT} = 1 \text{POCS} = 1)$	0.04

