6.3 SARS-CoV-2 infection endpoint

6.3.1 SARS-CoV-2 infection regardless of symptomology

Two definitions are considered for the SARS-CoV-2 any-infection endpoint regardless of symptomology. Definition 1 is the primary definition. Definition 2 is an exploratory definition.

- Definition 1: SARS-CoV-2 any-infection is defined in all participants who are:
 - baseline NAAT negative but tested NAAT positive at at least another post-baseline time-point, either triggered by symptom or performed at routine swabbing visits; OR
 - baseline NAAT positive but detected NAAT positive when either a) there are two consecutive negative NAAT results between the baseline and post-baseline positive swabs, or b) a positive post-baseline NAAT result is found at least 90 days after a single NAAT negative swab. Future analyses incorporating sequence information may also consider multiple occurrences; OR
 - baseline anti-N CLS negative but detected anti-N CLS positive post-baseline; OR
 - baseline anti-N CLS positive and detected anti-N CLS positive with anti-N IgG concentration at least 1.5 times higher than that at baseline. When the quantitative readout from the CLS assays is not available, this last criterion will not be considered.
- Definition 2: SARS-CoV-2 infection is defined only in participants with negative baseline SARS-CoV-2 status as defined in Section 5 based on the 3 tests (NAAT, POCS and CLS). A SARS-CoV-2 infection endpoint is any post-baseline SARS-CoV-2 infection detected positive by anti-N CLS, OR by NAAT (triggered by symptom, routine testing or other reasons).

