8.2.2 Exploratory analyses comparing hybrid and vaccine immunity groups among PLWH

For analyses including information from both the pre- & post-M6 stages, exploratory analyses of COVID-19 and severe COVID-19 between hybrid vs. vaccine immunity groups will consider two definitions of hybrid/vaccine immunity groups. The first is based on information at baseline and follows the same definition used in the Part A SAP for AG1 (Vaccine Immunity) and AG2.1 (Hybrid Immunity) and repeated below for easy reference.

1. AG1 (PLWH Vaccine Immunity; HIV+,SARS2-,2d) = PLWH; baseline SARS-CoV-2 naïve (negative for POCS, CLS, and NAAT); assigned 2 vaccinations pre-Month 6
2. AG2.1 (PLWH Hybrid Immunity; HIV+,SARS2+,1d) = PLWH; baseline POCS positive; assigned 1 vaccination pre-Month 6

The second definition of hybrid/vaccine immunity groups is based on a combination of baseline hybrid/vaccine immunity group information, Month 6 SARS-CoV-2 status and Month 6 recent SARS-CoV-2 infection status (see definitions in Section 5). Specifically, Month 6 Vaccine Immunity group includes a subset of AG1 participants who had no evidence of SARS-CoV-infection before or at Month 6 (i.e., Month 6 SARS-CoV-2 status = vaccine immunity); Month 6 Hybrid Immunity group includes a subset of AG2.1 participants who had no evidence of recent SARS-CoV-2 infection at Month 6 (i.e., Month 6 recent infection status = negative).

Comparing baseline hybrid vs. vaccine immunity groups among PLWH

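### NAAT-positive infections present at dose 1 can count as breakthrough COVID-19 in the hybrid group but almost never in the vaccine-only group, because counting starts the next day and no clearance rule applies

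*Protocol*

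**What the plan says.** **Who is in each group.** Protocol Table 6-1 defines the hybrid side by "SARS-CoV-2 positive is defined by seropositive and/or virus detection positive". For the vaccine-only side, "SARS-CoV-2 negative is defined by both seronegative and virus detection negative or by seronegative alone if missing virus detection test results". SAP 8.2.2 has the same structure: AG1 must be negative on point-of-care serology (POCS), central-lab serology (CLS) and NAAT, while AG2.1 is only "PLWH; baseline POCS positive; assigned 1 vaccination pre-Month 6". The baseline NAAT is taken at enrollment (Protocol Section 3, footnote 1), which coincides with the first vaccination (Protocol 9.3).

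**When counting starts.** The table in Protocol Section 3 has primary objectives 1 and 2 "counting endpoints starting 1 day after Month 0 dose until Month 6 dose". Protocol 6.4.3 agrees. The opening paragraph of Section 3 instead starts these objectives 14 days after the last pre-Month 6 dose. SAP exploratory analyses III-V count from 1 day after enrollment.

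**What happens to a baseline positive.** Protocol 9.6 sends them to the post-diagnosis schedule: "Participants found to have a positive SARS-CoV-2 NAAT test as part of a regularly scheduled visit outlined in Section 9.3 will also enter". This brings a daily symptom record, calls every other day, a Day 14 swab and further swabs until negative (Appendix J).

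**What makes a case.** SAP 6.1.1 and 6.1.2 ask for symptoms plus one positive swab after baseline. They require no intervening negative swab and no minimum interval from a baseline positive. SAP 6.3.1 has such a rule, but only for the any-infection endpoint: "baseline NAAT positive but detected NAAT positive when either a) there are two consecutive negative NAAT results between the baseline and post-baseline positive swabs". Its alternative limb is a positive at least 90 days after a single negative.

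**The concern.** Objectives 1 and 2 ask how often new COVID-19 occurs under hybrid and under vaccine-only immunity. Illness from an infection already under way at dose 1 does not answer that. One comparator is screened for such infections and the other is not, so any misattributed case falls almost wholly on the hybrid side. That inflates hybrid incidence and lowers the Group 1 vs 2 ratio.

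The route to a case is easy to trace. Take a hybrid participant with a positive swab and no symptoms on Day 1, a qualifying symptom on Day 3 and a still-positive swab on Day 14. Protocol 9.5 warns that several listed symptoms overlap with expected vaccine reactions, so the Day 3 symptom need not come from SARS-CoV-2. Under the SAP's CDC-based wording this person is a new case.

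Secondary objectives 1 and 2 and SAP exploratory analyses III-V use the same group definitions.

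**Working it through.** **1. The plan's own power figure.** Inputs from Protocol 6.3.1 and Table 6-2: 4,200 vs 8,400 participants, 5% six-month background incidence (half that in seropositives), vaccine efficacy 60% in Group 1, relative risk 2.0, two-sided exact binomial test at 0.05.

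- Group 1 events: 4,200 × 0.05 × 0.40 = 84.
- Group 2 events: 8,400 × 0.05 × 0.40 / 2 = 84.
- Total 168 before dropout; the table states 167.
- Share of events in Group 1: 1/3 under the null, 2.0/(2.0 + 2) = 0.5 under the alternative.
- Power with 167 events: 99.0% (stated 99%). With 125 events (efficacy 70%): 96.3% (stated 96%).

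**2. Baseline NAAT positives on the hybrid side.** SAP Table 1, Panel B ("Empirical probability that CLS or NAAT was positive conditional on POCS test result") gives 0.04 among POCS positives. Panel A agrees: 0.59 × 0.07 = 0.041, taking its printed zero for POCS-positive, CLS-negative people. At ceiling size, 8,400 × 0.04 = 336. The probability is pooled over HIV status, and 8,400 is a target size.

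**3. Leak into the vaccine-only side.** Participants without both NAAT and POCS results: 14,040 − 13,915 = 125 (0.9%). SAP Section 5 imputes a missing NAAT as negative. Suppose all 125 were negative on both serologies. Table 1 prints the NAAT-positive probability in that cell as 0, while its other entries imply 0.07 × (1 − 0.59)/(1 − 0.32) = 0.042. The expected leak is therefore between 0 and about 5 people.

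**4. Effect on the relative risk.** Let f be the share of the 336 who later meet the endpoint from the same infection. The documents do not give f, so these values are assumptions. Starting from 83.5 events in each group (167 in all), with denominators held fixed:

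RR = (83.5/4,200) / ((83.5 + 336f)/8,400) = 167/(83.5 + 336f)

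| f | Cases added | RR | Power |
|---|---|---|---|
| 0% | 0 | 2.00 | 99% |
| 2% | 6.7 | 1.85 | 98% |
| 5% | 16.8 | 1.67 | 91% |
| 10% | 33.6 | 1.43 | 67% |

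Starting from 125 events, RR is 2.00, 1.81, 1.58 and 1.30.

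**5. The same participant under each rule.** Day 1 positive swab, Day 3 symptom, Day 14 positive swab:

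- *Protocol 6.4.3, CDC-based endpoint.* The event is dated at the earlier of symptom and positive swab, hence Day 1. Counting starts the day after dose 1, and an endpoint diagnosed before counting excludes the participant. Result: excluded.
- *SAP 6.1.2, CDC-based endpoint.* The swab must be post-baseline, so the Day 14 swab is used. It is 11 days from the symptom, inside the 14-day limit, and the case is dated Day 3. Result: counted for the hybrid group.
- *SAP 6.1.1, COVE-based endpoint.* If the Day 3 symptoms meet the stricter list, the written criteria are met. Adjudicators decide whether it is a case and supply the date.
- *SAP 6.3.1, any-infection endpoint.* With no intervening negatives this is not a new infection.

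**The case against.** The strongest reply is that the protocol already deals with much of this. Its CDC dating rule together with its exclusion rule removes a Day 1 positive who develops symptoms within 14 days. COVE-based cases are symptom-triggered and adjudicated, and severe cases must be COVE-based, so a committee may well reject a known Day 1 infection. The pre-Month 6 SAP that governs objectives 1 and 2 is not among the documents and may hold an exclusion. Secondary objective 1 starts 14 days after the last dose and drops most early events. Participants with COVID-19 symptoms at a vaccination visit have the dose delayed, and a later swab must still be positive, so carry-over could be close to zero.

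Much of this stands. It limits the size of the problem but does not close the gap. The protocol's protection for CDC-based cases is undone by the SAP's post-baseline swab wording. The supplied SAP says in Section 6 that it uses the same COVID-19 definitions as the pre-Month 6 SAP. The adjudication charter is not supplied.

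Two stronger readings are tempting, and the documents do not support them:

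- *That the interim contrast of 7.1% vs 2.2% a year (ratio 3.2) is materially understated.* Nothing shows that the 2.2% contains such cases. Protocol 2.1 says the study had used the COVE approach up to then, which closes the easiest route (one reaction symptom under the CDC-based criteria).
- *That POCS-negative, NAAT-positive people add many more to the hybrid side.* They were assigned two doses, whereas Protocol 6.4.3 compares one-dose Group 2 and AG2.1 requires POCS positivity. They would enter only if the one-or-two-dose wording of Table 6-1 governs.

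**Conclusion.** The point holds as a one-sided gap of unknown size. Baseline NAAT positivity is allowed on the hybrid side and screened out on the vaccine-only side apart from a handful of missing results. Primary counting begins the next day, and COVID-19 and severe COVID-19 have no clearance rule in the documents supplied. Infections that are incubating but NAAT negative on Day 1 can occur in both groups and are not part of this asymmetry.

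The direction is clear. Added hybrid cases lower the Group 1 vs 2 ratio, which means toward 1 when the true ratio exceeds 1. From a true 2.0 with 167 events, the estimate runs from 2.0 (no carry-over) to 1.43 (10%). This rests on the assumed f, the ceiling sample size and the pooled 4%. The bias works against hybrid immunity, so it cannot explain the reported hybrid advantage; what it can distort is the size of the relative risk. Secondary objective 1 lessens it but may not remove it, since swabbing continues until negative.

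Apart from size, the documents give opposite answers for the same participant and two different start dates for the primary objectives. Both need settling.

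**What to change.** 1. Reconcile the start of counting (opening text of Protocol Section 3 against its table and 6.4.3), the number of doses in Group 2 (Table 6-1 against 6.4.3), and the CDC event dating with its exclusion (Protocol 6.4.3 against SAP 6.1.2).
2. For participants who are NAAT positive at baseline, apply the clearance rule of SAP 6.3.1 to COVID-19 and severe COVID-19. Almost every case it removes will be a hybrid case, so report how many it removes.
3. For primary objectives 1-2, secondary objectives 1-2 and exploratory analyses III-V, add a sensitivity analysis, specified before it is run, restricting both groups to baseline NAAT-negative participants (hybrid = seropositive and NAAT negative).
4. Keep the current cohort as the main analysis. Interim results are known, and replacing it now would be a change made in the direction that enlarges the ratio.

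The cost is wording in both documents and one extra analysis on data already collected. That analysis has about 4% fewer Group 2 participants: 8,400 − 336 = 8,064 at ceiling size.
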